Evaluation of antiviral indications and therapeutic effect by liver biopsy combined with clinical trial parameters on chronic HBV infection with different transaminase levels

Study Protocol with Statistical Analysis Plan (SAP) and Informed Consent Form (ICF)

October 25, 2018

Evaluation of antiviral indications and therapeutic effect by liver biopsy combined with clinical trial parameters on chronic HBV infection with different transaminase levels

Study Protocol
(Pages 2-5)

October 25, 2018

Study Protocol

Study titled 'Evaluation of antiviral indications and therapeutic effect by liver biopsy combined with clinical trial parameters on chronic HBV infection with different transaminase levels' was approved by the First Affiliated Hospital of Xi'an Jiaotong University of Medicine Clinical Researches Ethics Committee meeting on 10/19/2018 with approval number: XJTU1AF2018LSK-146.

The patients or legal representatives of the children who participated in the study were informed about the aim and the programs to be applied throughout the study. Volunteer Information Form has been signed and approved in accordance with the standards deemed appropriate by the First Affiliated Hospital of Xi'an Jiaotong University of Medicine Clinical Researches Ethics Committee (This form can be seen on Informed Consent Form (ICF) section). The study was conducted in accordance with the Declaration of Helsinki.

Hypothesis of the Study

H0: Initiating treatment is not recommend for the patients with ALT <2ULN, high viral load, because some studies considered that the potential harms of long-term therapy, including cost, low response rates, drug adverse effects and development of resistance, outweigh its benefits.

H1: Initiating treatment is recommend for the patients with ALT <2ULN, high viral load, because some studies considered that high levels of serum HBV DNA (>10⁴copies/ml) are associated with a high risk of hepatocellular carcinoma (HCC) and the histological activity and HBV-specific immune responses do also occur in this

phase.

Inclusion Criteria

(1)Patients with a history of chronic HBV infections,defined as those in whom presence of serum hepatitis B surface(HBsAg) for more than 6 months.

(2)All patients had underwent a liver biopsy.

(3)All patients signed the informed consent.

(4)No history of interferon or Nucleoside analogue treatment.

Exclusion Criteria

(1)Co-infection with human immunodeficiency virus(HIV),hepatitis A virus(HAV),hepatitis C virus(HCV),hepatitis D virus(HDV) and/or hepatitis E virus(HEV).

(2)Decompensated cirrhosis.

(3)History of liver transplantation.

(4)History of hepatocellular carcinoma(HCC).

(5)Having received antiviral treatment.

(6)Taking immunoregulation drugs such as cytotoxic agents and hormones.

(7)Use of hepatotoxic drugs or regular consumption of alcohol.

(8)Autoimmune disease or antinuclear antibody titers higher than 1:160.

(9)And other chronic liver disease.

[figure not shown]
(10)Incomplete data.

Applied Evaluations

[figure not shown]
Response indexes as the follows: virological response(HBV DNA below the

detection limit);HBsAg response(HBsAg decline \geq 0.5log₁₀ IU/ml);HBeAg seroconversion(HBeAg loss and HBeAb appearance);biochemical response(ALT normalization);LSM response(LSM decrease as at least a 1-kPa).

Research programme

Research group

Evaluation of antiviral indications and therapeutic effect by liver biopsy combined with clinical trial parameters on chronic HBV infection with different transaminase levels

Statistical Analysis Plan (SAP)

(Pages 6-7)

October 25, 2018

Statistical Analysis Plan (SAP)

The statistical program Statistical Package for Social Sciences (SPSS) Version 20.0 (SPSS Inc., Chicago, IL, USA) was used in the data analysis of the study. The p value of $p < 0.05$ was considered to be statistically significant in the data analysis. Continuous quantitative variables were expressed as mean \pm standard deviation (SD) for normal distributions or median and interquartile range (IQR) (25th-75th percentile) for abnormal distributions, which were assessed with an independent samples T test or the Mann-Whitney U test as comparison of two sets of samples while comparison of multiple samples were assessed with ANOVAs or Kruskal-Wallis tests. Repeated measures data of general linear model were used to calculate variation trend between treated and untreated follow-up patients. Categorical variables were expressed as percentages that were analyzed using the χ^2 test, such as gender, HBV genotype, ALT, HBsAg, HBeAg, HBeAb, HBcAb and LSM.

The receiver operating characteristic (ROC) curve was plotted in order to find the most appropriate HBV DNA, HBsAg, HBeAg cutoff value for diagnosis of patients with ALT < 2 ULN who are chronic HBV infection or chronic hepatitis B.

Univariate logistic regression and multivariate forward stepwise logistic regression were used to assess the incidences of antiviral responses, such as HBV DNA response, serological responses, biochemical response

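### Are ALT normalization and HBeAg seroconversion distorted by patients who could not respond, and LSM response by where patients start?

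*Combined protocol and SAP*

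**What the plan says.** Under *Applied Evaluations* the protocol defines five response indexes. Three matter here: "HBeAg seroconversion(HBeAg loss and HBeAb appearance);biochemical response(ALT normalization);LSM response(LSM decrease as at least a 1-kPa". None carries a baseline requirement or a denominator.

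*Inclusion Criteria* asks for "presence of serum hepatitis B surface(HBsAg) for more than 6 months", a liver biopsy, consent and "No history of interferon or Nucleoside analogue treatment". Neither these criteria nor the readable exclusions require raised ALT, HBeAg positivity or a minimum LSM. Under *Hypothesis of the Study*, H1 reads "Initiating treatment is recommend for the patients with ALT <2ULN, high viral load", which limits ALT only from above.

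In the *Statistical Analysis Plan (SAP)*:
- "Categorical variables were expressed as percentages" and compared by chi-square; HBeAg, HBeAb, ALT and LSM are among the examples.
- ROC curves seek the "HBV DNA, HBsAg, HBeAg cutoff value for diagnosis of patients with ALT < 2 ULN".
- "Repeated measures data of general linear model were used to calculate variation trend between treated and untreated follow-up patients".
- Univariate and "forward stepwise logistic regression were used to assess the incidences of antiviral responses, such as HBV DNA response, serological responses, biochemical response". The text available here stops at that point, in mid-list.

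A figure just before the response definitions is not shown, and the headings *Research programme* and *Research group* have no readable content.

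**The concern.** A patient whose ALT is already normal cannot normalize it, and a patient without HBeAg cannot lose it. The study population plausibly contains both kinds, and the group named in the hypotheses may include many with normal ALT. If they stay in the denominator as non-responders, each rate mixes treatment response with baseline case mix. A real difference would shrink. If the mix differed between treated and untreated patients, for whom no randomisation is described, a difference could appear where none exists.

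In a logistic model of seroconversion, HBeAg-negative patients could contribute only non-events, so a marker of baseline HBeAg status might pass for a predictor of response.

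LSM raises a related worry. An absolute fall of 1 kPa is easier to reach from a higher starting value, so unequal baselines would shift the responder rate.

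**Working it through.** The readable documents give no response rate, baseline mix, sample size or measurement error, so there is no figure to reproduce. Every input below is an assumption; the results show what would follow, not what will.

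**1. Dilution of ALT normalization.** Let *f* be the fraction normal at baseline and *p* the true response among those at risk. If normal patients count as non-responders, the observed rate is (1 − *f*)*p*. With *p* = 70% and 40% and the same *f* in both groups:

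| *f* | Group 1 | Group 2 | Difference (points) | Odds ratio |
|---|---|---|---|---|
| 0% | 70% | 40% | 30 | 3.50 |
| 10% | 63% | 36% | 27 | 3.03 |
| 30% | 49% | 28% | 21 | 2.47 |
| 50% | 35% | 20% | 15 | 2.15 |

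This can arise only below 2 ULN, since everyone at or above that level has raised ALT.

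**2. Unequal mix, and which way it pushes.** Take *f* = 30% and 50%, with a true 70% in both groups.
- Normal patients counted as non-responders: 0.7 × 0.7 = 49% and 0.5 × 0.7 = 35%. Odds ratio (0.49/0.51)/(0.35/0.65) = 1.78.
- Patients normal throughout counted as responders, *f* + (1 − *f*)*p*: 0.30 + 0.49 = 79% and 0.50 + 0.35 = 85%. Odds ratio (0.79/0.21)/(0.85/0.15) = 0.66.

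The true value is 1.0. The direction depends on a coding the readable text does not state.

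**3. Does the plan make this comparison?** Treated versus untreated is named once, for the repeated-measures trend. The chi-square examples include no response index. The logistic sentence does not name treatment as a predictor, and those models could be confined to treated patients. The odds ratios in steps 1 and 2 therefore describe a contrast that the readable text does not specify.

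**4. The marker example.** Suppose half the patients are HBeAg-negative, 20% of HBeAg-positive patients seroconvert, and a marker is present in 70% of HBeAg-positive and 30% of HBeAg-negative patients but unrelated to response among those at risk. With everyone analysed, response is 0.2 × 0.35/0.50 = 14% with the marker and 0.2 × 0.15/0.50 = 6% without. The odds ratio is (0.14/0.86)/(0.06/0.94) = 2.55. A single-variable test would give p < 0.05 in about 26%, 47% or 76% of studies at N = 100, 200 or 400.

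Those are not stepwise selection rates. Take the expected tables at N = 100:
- Marker, 7/50 against 3/50: chi-square = 100 × (7×47 − 3×43)² / (50×50×10×90) = 1.8.
- Baseline HBeAg, 10/50 against 0/50: chi-square = 100 × (10×50 − 0×40)² / (50×50×10×90) = 11.1.

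If baseline HBeAg is a candidate, it would usually enter first. Within HBeAg-positive patients the marker then shows 7/35 against 3/15, which is 20% in both, so nothing remains to select. A row with no events at all would also alert the analyst that these patients are not at risk.

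**5. LSM.** Assume baselines of 6 and 8 kPa, a 10% fall from each, per-reading SD 0.5 kPa and between-patient SD of true change 0.5 kPa. The SD of observed change is √(2 × 0.25 + 0.25) = 0.866. The chance of a fall of at least 1 kPa is P(Z > (1 − 0.6)/0.866) = 32% and P(Z > (1 − 0.8)/0.866) = 41%. The dependence on baseline is real, but the nine-point gap needs an assumed 2-kPa imbalance, and no readable model takes LSM response as its outcome.

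**The case for a change.** The best case for a change is that it costs a line of text, needs no data beyond what the definitions already require, and could improve power. With an assumed 100 per group, true rates of 60% and 30%, and 60% of patients at risk, analysing everyone as described gives power 0.82; analysing only the 60 per group at risk gives 0.92. Step 2 adds that two analysts coding the not-at-risk patients differently would obtain opposite results.

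Two parts of this stand. The readable text does not state the denominators, and a reader of the results will need them. The power comparison is also sound on its inputs.

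It does not follow that the plan is wrong. *Loss*, *appearance* and *normalization* each describe a move away from a starting state, so the at-risk set is implicit in the definitions; both codings in step 2 require an analyst to set that aside. The readable text ties no sample size or decision rule to these rates. The missing figure, the two empty headings and the truncated regression sentence are where a denominator could be given, and text absent from this copy cannot be treated as absent from the plan.

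On LSM, a fixed absolute threshold is easy to interpret, and the repeated-measures model can carry continuous LSM if it is among its outcomes. Whether to adjust change for baseline in unrandomised groups is a matter on which statisticians differ, because the adjusted and unadjusted analyses answer different questions.

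**Conclusion.** The concern identifies a detail left unstated in the readable text, not a rule that gives a wrong answer. No change to the plan follows. Competent analysts would take ALT normalization among patients with ALT above ULN at baseline, take seroconversion among those HBeAg-positive and HBeAb-negative at baseline, and print the number at risk beside each rate.

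The effect cannot be sized from the documents. The illustrative odds ratios (3.50 falling to between 3.03 and 2.15; a null value reading 1.78 or 0.66) rest wholly on assumed mixes and rates, and on a comparison of responder rates that the readable text does not specify. The marker percentages do not measure stepwise selection, and the LSM point is a choice of endpoint.

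Confidence is limited by the unreadable parts. The conclusion would change if they stated that not-at-risk patients are counted as non-responders, or as responders.

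### The SAP's one readable treated-versus-untreated comparison states no baseline adjustment and no link to the H0/H1 patients; if treatment followed measured ALT, part of an ALT trend would be regression to the mean

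*Combined protocol and SAP*

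**What the plan says.** Under Hypothesis of the Study, H1 reads "Initiating treatment is recommend for the patients with ALT <2ULN, high viral load", and H0 is the opposite recommendation for the same patients. The reasoning given for H1 mentions HBV DNA above 10^4 copies/ml.

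The population is wider. The title covers a range of transaminase levels, and no readable eligibility criterion limits ALT or HBV DNA. Inclusion criterion 2 says "All patients had underwent a liver biopsy" and criterion 4 says "No history of interferon or Nucleoside analogue treatment", so whether a patient counts as treated is settled at or after entry.

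In the SAP, the only sentence that names a treated-versus-untreated contrast is "Repeated measures data of general linear model were used to calculate variation trend between treated and untreated follow-up patients". It states no outcome, visit times, baseline covariate or patient subset. The SAP uses the ALT <2ULN restriction in one place, the ROC analysis, which seeks a "cutoff value for diagnosis of patients with ALT < 2 ULN who are chronic HBV infection or chronic hepatitis B". The only readable multivariable method is a regression in which "multivariate forward stepwise logistic regression were used to assess the incidences of antiviral responses"; that text breaks off mid-sentence.

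Applied Evaluations counts ALT normalisation as the biochemical response. The content under Research programme and Research group is not shown, so definitions of the groups and of allocation may be there. They are not treated as missing here.

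**The concern.** A group-by-time term in a repeated-measures GLM compares changes from baseline. Including the baseline visit as one of the responses does not adjust for a baseline difference between groups. If patients were more likely to be treated because their measured baseline ALT was high, part of that high reading was transient. The treated group then falls further than the untreated group with no drug effect, and the model reports the difference as a treatment trend.

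An ALT benefit produced this way could be read as support for H1. If all ALT levels were analysed together, part of it would come from patients at or above 2ULN, about whom H0/H1 say nothing.

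**Working it through.** The documents give no sample size, SD, visit correlation or treatment rule, so there is no figure to reproduce. All inputs below are assumed, except the 0.05 significance level (SAP), the 2ULN cut and the 10^4 copies/ml level (H0/H1). The true treatment effect is zero throughout.

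**Mechanism, two time points.** With correlation ρ between visits and a treated-minus-untreated baseline difference D in log ALT, bias in change = −(1 − ρ) × D. Assume ln(ALT/ULN) has SD 0.7 and geometric mean 1.3 ULN, with treatment probability logistic in baseline ln ALT, centred at 2ULN.
- ρ = 0.7, slope 1 per SD: D = 0.583, bias = −0.3 × 0.583 = −0.175, and exp(−0.175) = 0.84. Treated ALT appears 16% lower.
- Slopes 0.5 to 2: spurious ratios are 0.85 to 0.65 at ρ = 0.5, 0.91 to 0.77 at ρ = 0.7 and 0.97 to 0.92 at ρ = 0.9.
- Slope 0: ratio about 1.00, false positives 4.0%-4.9%.

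**Restriction alone.** Within ALT <2ULN, the −0.175 becomes −0.091, so 0.091/0.175 = 52% of the bias remains. Across the nine settings with a non-zero slope, 51% (0.030/0.059) to 54% (0.047/0.087) remains. Under a rule that treats everyone at or above 2ULN, 36%-39% remains (from the assumptions in the next step).

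**Rejection rates, baseline plus three follow-up visits.** There were 2,000 simulated cohorts per setting (Monte Carlo error about 0.5 points near 5%). Assumed: log10(ALT/ULN) mean 0.15, between-patient SD 0.25, within-patient SD 0.08, 0.10 or 0.15, so ρ = 0.0625/(0.0625 + SD²) = 0.91, 0.86 or 0.74; biopsy grade 0-4 with latent correlation 0.5 with true ALT; log10 HBV DNA SD 2, correlation 0.2 with ALT, 75% above 10^4; HBeAg status dependent on HBV DNA. Slopes are logistic, per SD. False-positive rates (%) at N = 200, for the three within-patient SDs:

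| What drove treatment | Analysis | Rate |
|---|---|---|
| Baseline ALT, slope 0.7 | pooled, unadjusted | 15 / 20 / 35 |
| Baseline ALT, slope 1.5 | pooled, unadjusted | 35 / 51 / 83 |
| All ≥2ULN, slope 1.0 below | pooled, unadjusted | 39 / 57 / 89 |
| ALT 0.7 plus biopsy 1.0 | pooled, unadjusted | 10 / 14 / 22 |
| Biopsy alone, slope 1.5 | pooled, unadjusted | 5 / 6 / 5 |
| Earlier ALT reading | pooled, unadjusted | 5 / 4 / 4 |
| Baseline ALT, slope 1.5 | H0/H1 patients, unadjusted | 8 / 10 / 15 |
| ALT 0.7 plus biopsy 1.0 | H0/H1 patients, unadjusted | 5 / 5 / 5 |
| Biopsy alone, slope 1.5 | H0/H1 patients, baseline ALT only | 11 / 14 / 21 |
| Earlier ALT reading | H0/H1 patients, full covariate set | 20 / 25 / 31 |
| Earlier ALT reading | full set plus that reading | 6 / 5 / 5 |

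Over all ALT-driven rules, the unadjusted test gives 15%-89% pooled (ALT 3%-19% lower) and 6%-15% within the H0/H1 patients (ALT 2%-9% lower). At N = 100 these are 9%-57% and 6%-9%. The full covariate set gives 4%-6% under all nine rules whose drivers are in the model, which is expected by construction. An HBsAg-like outcome whose error is unrelated to treatment stays at 4%-6%.

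**Why baseline ALT alone is not enough.** Where treatment depended only on baseline ALT, that adjustment brings the bias to at most 0.002 on the log scale. Where biopsy led treatment, single-visit ALT only partly captures the true ALT difference between groups. Treated patients then look 2%-10% worse, with 9%-29% false positives at N = 200. Adding HBV DNA and HBeAg without biopsy does not help (11 / 14 / 21).

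**Cost in patients.** The ALT cut keeps 70%-72% of the assumed cohort. Both cuts keep about 40%, 51% or 63% if 60%, 75% or 90% exceed 10^4 copies/ml. At 75%, the smallest ALT reduction detectable with 80% power is about 15%-30% at N = 100 and 11%-22% at N = 200.

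**The case against.** The strongest reply is that several conditions must hold together and the documents state none of them. The GLM sentence does not say that all ALT levels are pooled, and the groups may be defined in content not shown. ALT is not named as its outcome: the SAP lists ALT among the variables for the χ² test and places the biochemical response under logistic regression. Allocation is not visible. The title, "Evaluation of antiviral indications and therapeutic effect by liver biopsy combined with clinical trial parameters", suggests a mixed basis for treatment, and under the mixed rule the H0/H1 patients show about 5% with no adjustment. The proposed model also depends on the mechanism, because it is biased if an unmodelled earlier ALT reading drove treatment, while the pooled unadjusted test then is not.

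All of that stands, and it limits the claim. A reader might infer that the plan pools all patients and that its ALT result is biased. The documents do not support this, because neither the grouping nor the treatment rule can be read. A reader might also infer that most of the artefact comes from patients at or above 2ULN. Under graded ALT rules about half remains after restriction; only a strict threshold removes more.

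The reply does not remove two things. The sentence states no adjustment and no link to H0/H1, however patients were allocated. The stepwise logistic regression concerns response incidence, forces in no readable treatment or baseline term, and would not correct the GLM.

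**Conclusion.** The point holds conditionally, with medium confidence, and should be fixed. As readable, the analysis closest to the question in H0/H1 is neither adjusted for baseline nor tied to those patients. The bias requires non-random allocation, ALT as a modelled outcome and treatment that partly followed measured baseline ALT. The sizes above are ranges under assumed inputs, not estimates for this study. No inflation of the pooled test is expected if treatment was unrelated to ALT or followed biopsy alone.

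It would also go too far to say that the adjusted model is right whatever guided treatment. It protects against drivers that are in the model, and other unmeasured confounding remains.

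**What to change.** 1. State how patients came to be treated or untreated, and which measurements informed it. If they were not randomised, describe the comparison as observational.
2. For the comparison used to address H0/H1, analyse patients with baseline ALT <2ULN and the study's own high-viral-load level.
3. Model the follow-up visits only, with the baseline value of the outcome, ALT, log10 HBV DNA, HBeAg status and the biopsy result forced in rather than selected stepwise. Add any earlier reading that informed treatment.
4. Do not adjust for baseline ALT without the biopsy result. If biopsy cannot be entered, report the comparison as descriptive.
5. Show the unadjusted trend alongside, labelled descriptive.

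A whole-cohort model with a treatment-by-ALT-group interaction is an alternative only if enough patients at or above 2ULN are untreated. At N = 100 with ALT slope 1.5, only 47%-62% of simulated cohorts had at least five treated and five untreated there, and under the threshold rule the interaction cannot be estimated.

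The work is SAP wording and one re-specified model. ALT, HBV DNA and HBeAg are already named in the SAP and every patient has a biopsy, although its scoring is not shown in the readable text. Restriction loses precision even if allocation was random.

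### If there are two or more follow-up visits, the repeated-measures model uses only patients seen at every one; a mixed model on all visits, with the incomplete-data exclusion limited to baseline, is a cheap improvement

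*Combined protocol and SAP*

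**What the plan says.** The Statistical Analysis Plan gives one sentence to change over time between the groups: "Repeated measures data of general linear model were used to calculate variation trend between treated and untreated follow-up patients". The software is "Statistical Package for Social Sciences (SPSS) Version 20.0".

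The only visible text that touches missing data is in the Exclusion Criteria: "10)Incomplete data". It does not say whether baseline or follow-up data are meant. A biopsy is already an entry condition under the Inclusion Criteria: "2)All patients had underwent a liver biopsy".

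The visible text gives no number or timing of visits, sample size, expected attrition, imputation rule or mixed model, and does not name the outcomes that enter the repeated-measures model. Two figures are not shown, and the text stops in the middle of the sentence on logistic regression.

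**The concern.** A repeated-measures general linear model takes one row per patient and drops any patient who lacks a modelled visit. That is a general property of the procedure, not a statement in the documents. A patient seen at baseline and at all but one follow-up visit would contribute nothing.

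If criterion 10 is read to include follow-up, it excludes the same patients first, on post-baseline information, and the model has nobody further to drop. If it means baseline only, just the modelling point remains. Changing the model alone, or the criterion alone, can therefore leave the loss in place.

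This is the only visible comparison of treated and untreated patients over time, so it bears on the question posed in the study hypothesis. What could be lost is precision. The estimate could also shift if leaving depends on the observed marker differently in the two groups.

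**Working it through.** **Plan's own figure.** There is none to reproduce. Every input below is an assumption except the 0.5 log10 HBsAg response threshold under Applied Evaluations, which only sets the scale.

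**Assumed model.** Baseline plus K equally spaced follow-up visits; random-intercept SD 0.5; residual SD 0.2; SD of individual total change 0.3 or 0.6; mean change -0.60 log10 treated and 0 untreated. The target is the group difference in change from baseline to last visit.

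**Precision.** With a fraction m missed per visit, the share of complete patients is (1-m)^K, so the complete-case standard error (SE) relative to full data is (1-m)^(-K/2). The share is the same whether visits are missed independently or patients leave for good. For K=3 and m=0.10, the share is 0.9^3 = 0.729 and the ratio is 0.9^(-1.5) = 1.171. The mixed-model ratio comes from the expected information summed over missingness patterns; ranges cover the two SDs of change. SE increases at m=0.10:

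| Follow-up visits | Complete patients | Complete cases | Mixed model, independent misses | Mixed model, permanent dropout |
|---|---|---|---|---|
| 1 | 90% | +5% | +5% | +5% (same pattern) |
| 2 | 81% | +11% | +2-3% | +7-9% |
| 3 | 73% | +17% | +2-3% | +10-12% |
| 4 | 66% | +23% | +1-2% | +12-16% |

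With independent misses at m=0.05, two visits give +5% against +1-2%, and three to four give +8-11% against about +1%. At m=0.15 the figures are +18% against +4-6%, and +28-38% against +2-4%. Permanent dropout with four visits at m=0.15 gives +38% against +20-26%.

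**Bias, first illustration.** Only untreated patients with a rising observed marker leave selectively: logit P(leave) = a + s × last observed change in the untreated, a alone in the treated, with three or four visits. The odds ratio (OR) per log10 is e^1 = 2.7 or e^3 = 20. Attenuation is 1 - |estimate|/0.60.

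| a, s | Untreated retained | Complete-case difference | Attenuation |
|---|---|---|---|
| -3.5, 1 | 88-91% | -0.596 to -0.577 | 1-4% |
| -3.5, 3 | 83-89% | -0.582 to -0.509 | 3-15% |
| -2.2, 1 | 64-72% | -0.584 to -0.530 | 3-12% |
| -2.2, 3 | 58-68% | -0.543 to -0.391 | 10-35% |

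With non-selective dropout the complete-case result is -0.598 to -0.603, so there is no bias. With one follow-up visit this illustration also gives none.

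**Direction.** A second set of assumptions has 100 per group, within-patient correlation 0.6, a true difference of -0.50 SD, and untreated patients with a high previous level leaving more often. With two to four visits, complete cases give -0.53 to -0.55, away from zero, and all-visit likelihood gives -0.49 to -0.51. Here leaving depends on the level, baseline included, so a small shift also appears with one visit. The point does not rest on that.

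**Covariance in the replacement model.** With equal spread in both groups, a common covariance returns -0.598 to -0.603 in the first illustration. Now let the SD of change be 0.9-1.2 treated and 0.3 untreated, with a=-2.2, s=3 and three or four visits. A common covariance then gives -0.64 to -0.68 against -0.60, an overstatement of 0.04/0.60 = 7% to 0.08/0.60 = 13%. Complete cases give about -0.52 to -0.55. A group-specific covariance gives -0.60.

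**Leaving on an unseen value.** With equal spread, untreated patients who leave because of an unobserved rise attenuate the mixed-model result by 1-2% (light dropout, OR about 3) to 12-23% (heavy, OR about 20), against 2-6% to 18-51% for complete cases.

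**The case against.** The strongest objection is that no visible trial fact triggers the concern. The schedule and a missing-data rule may stand in figures or text not available here, and with a single follow-up visit there is almost nothing to gain. This stands, and is why the point is conditional. The SAP's wording, "variation trend between treated and untreated follow-up patients", fits several visits better than one, but does not prove them.

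Second, independently missed visits are the pattern most favourable to the mixed model. This also stands: under permanent dropout roughly half or less of the standard-error penalty at three or four visits is recovered, and less at two.

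Third, a mixed model is not accurate by default. A common covariance can overstate the difference when spread differs by group, so the fix asks for a group-specific one.

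Fourth, criterion 10 sits among the eligibility rules, where a baseline reading is natural. That is fair, but the wording does not say so, and settling it takes one line.

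Fifth, the change has consequences elsewhere. The logistic regressions of response need a follow-up outcome, and virological response is defined by the detection limit. Both are added to the cost.

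A reader might infer that the planned comparison is biased towards no effect. The documents do not support this: they show no attrition, and the direction reverses with who leaves. A reader might also infer that the plan has no missing-data rule. With text and figures unavailable, one can say only that none is visible.

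**Conclusion.** The concern holds as a conditional, cheap improvement, with medium confidence. If there are two or more follow-up visits and some are missed, the planned model discards collected data. At an assumed 10% per visit, the avoidable part of the standard-error increase is most of 11-23% with scattered misses, and a smaller part with permanent dropout. Bias is possible but not shown: it is nil under missing completely at random, and otherwise depends on who leaves and how strongly. The 1-4% to 10-35% attenuation range belongs to one assumed mechanism and is not an estimate for this trial.

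The grade is no higher because the visit count and attrition are not visible, criterion 10 can be read as baseline only, and no randomisation is described, so confounding between the groups remains under either model.

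**What to change.** Make both changes together.

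1. Limit criterion 10 to missing baseline biopsy or baseline laboratory data needed to classify the patient.
2. Replace the repeated-measures general linear model with a likelihood-based mixed model on all available visits: baseline as one of the responses; group, visit and group-by-visit effects; and an unstructured covariance allowed to differ by group. Equivalently, fit the model separately in each group and contrast the changes, with SE = √(SE₁² + SE₂²). Report attrition by group.

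Baseline is kept as a response, not a covariate, so that the target remains the difference in trend. With the assumed SDs the covariate slope would be 0.25/(0.25 + 0.04) = 0.862, and a 0.5 log10 baseline gap would move the estimate by (1 - 0.862) × 0.5 = 0.069 log10.

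**Cost.** One eligibility line and one SAP sentence on the model, no new patients or visits, and the same package's mixed-model procedure. Two further rules are needed: how the logistic regressions treat patients without the follow-up outcome, and how HBV DNA below the detection limit is censored or transformed.

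**Downsides.** The model assumes data are missing at random. It recovers less precision when dropout is permanent, offers essentially no gain with one follow-up visit, and does not remove confounding.
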